9.1. Acquisition and accountability

State how the study intervention and control product will be provided to the investigator. Describe plans about how and by whom the study intervention will be distributed, including participation of a drug repository or pharmacy, and plans for disposal of expired or return of unused product.

N/A

9.2. Formulation, Appearance, Packaging, and Labeling

Describe the formulation, appearance, packaging, and labeling of the study intervention and control product, as supplied. Information in this section can usually be obtained from the IB or the package insert, or device labeling. This section should include the name of the manufacturer of the study intervention and control product.

N/A

9.3. Product Storage and Stability

Describe storage and stability requirements (e.g., protection from light, temperature, humidity) for the study intervention and control product. For studies in which multi-dose vials are utilized, provide additional information regarding stability and expiration time after initial use (e.g., the seal is broken).

N/A

9.4. Preparation

Describe the preparation of the study intervention and control product, including any preparation required by study staff and/or study participants. Include thawing, diluting, mixing, and reconstitution/preparation instructions in this section. For devices, include any relevant assembly or use instructions.

N/A

10. Study Intervention Additional Details

10.1. Measures to Minimize Bias: Randomization and Blinding

This section should contain a description of randomization and blinding procedures (if applicable to the study design). It should include a description or a table that describes how study participants will be assigned to study groups, without being so specific that blinding or randomization might be compromised. Plans for the maintenance of trial randomization codes and appropriate blinding for the study should be discussed. The timing and procedures for planned and unplanned breaking of randomization codes should be included. Include a statement regarding when unblinding may occur and who may unblind. Provide the criteria for breaking the study blind or participant code. Discuss the circumstances in which the blind would be broken for an individual or for all participants (e.g., for serious adverse events (SAEs)). Indicate to whom the intentional and unintentional breaking of the blind should be reported.

- Subjects (N=40) will be randomized in a 1:1 ratio into two groups using a computer program that generates random numbers to receive modified Sodium Watchers intervention. Everyone will receive a baseline and end of study visits.
- Subjects randomized to (Group 1) intervention group (IG) will be asked to follow the modified Sodium Watchers Program intervention along with goal setting for low salt foods. Each subject will be registered to assign a unique ID in the Connected Health Platform developed by the Center on Smart and Connected Health Technologies at UT Health Science Center San Antonio (UTHSCSA) and each account from the individuals' wireless and wearable devices (Fitbit and BP monitor) will be connected to his or her unique ID through this platform. Subjects will be instructed to log their activities in real-time, including food intake and in-home BP monitoring using Fitbit and accompanied mobile app and BP monitor. Through the Connected Health Platform, the Fitbit app and BP monitor will transmit the data of the intervention group to the research team. The PI will remotely track user engagement and will call participants if they fail to measure any behavior for 3 days using "Sync function" or subscribing to "Alerts" which will alert us when a user has an inactive or invalid status.
- Subjects randomized to (Group 2) control group (CG) will be asked to follow usual care which is based on their routine medical and nursing care for pre-hypertension that consists of a recommendation to follow SRD and take medications as prescribed. The subjects will receive wireless and wearable devices (Fitbit wristband, BP monitor). Each subject will be registered to assign a unique ID in the Connected Health Platform at the baseline and each account from the individual's wireless and wearable devices (Fitbit and BP monitor) will be connected into their unique ID through this platform. Subjects will be instructed to log their activities in real-time, including food intake and in-home BP monitoring using Fitbit and accompanied mobile app and BP monitor. Through the Connected Health Platform, the Fitbit app and BP monitor will transmit the data of the IG to the research team. The intervention nursing research assistant will remotely track user engagement and will call participants if they fail to measure any behavior for 3 days using "Sync function" or subscribing to "Alerts" which will alert us when a user has an inactive or invalid status.
- Both Group 1 and Group 2 participants will receive information sessions.

10.2. Study Intervention Compliance

Define how adherence to the protocol (e.g., administration of study intervention, use of device,) will be assessed, and verified (if applicable, e.g., plasma assays, electronic monitoring devices, daily diaries).

All research staff involved in this study will be trained to adhere to the study protocol when performing relevant study activities. They will have access to the most current protocol. In addition, mobile health devices will be used in Control group to monitor their compliance with device usages and their dietary intervention adherence. Further, we will take several steps to minimize participant attrition including providing reimbursement and collecting multiple contact information (cell phone, home phone, email addresses) from the participants in order to remind them of the scheduled visits and intervention sessions. We will also provide periodic updates and send thank you note to participants to remind them of the study and the importance of their support. The information gained from the pilot project will inform future SRD interventions to improve SRD adherence and cardiovascular outcomes.

10.3. Permitted Concomitant Therapy

This section should be consistent with the medication restrictions in the inclusion/exclusion criteria previously listed. Describe how allowed concomitant therapy might affect the outcome (e.g., drug-drug interaction, direct effects on the study endpoints).

Participants in both groups won't be restricted from their previous antihypertensive medications. All relevant data, including medication usage and other forms of therapy, will be considered when conducting data analysis wherever necessary to avoid or minimize its effects on study endpoints.

10.4. Rescue Medicine

List all medications, treatments, and/or procedures that may be provided during the study for "rescue therapy" and relevant instructions.

N/A, no rescue medicine

11. Study Intervention Discontinuation

11.1. Discontinuation of Study Intervention

Describe the criteria for discontinuing the study intervention (e.g., halting rules), including any monitoring test(s) and associated clinical decision point(s). Include reasons for temporary discontinuation of the study intervention (e.g., type and quantity of adverse events), clearly stating the length of time, if applicable, and describe the data to be collected at the time of study intervention discontinuation and approaches for restarting administration of or re-challenging with study intervention.

This is expected to be a minimum risk study with behavioral diet interventions. All participants will be allowed to discontinue the study at any time. In addition, participants' blood pressure will be monitored by mobile device. Should any unusual readings (e.g.,

unusual low/high blood pressure), which may threaten participant's health, are identified for a participant, the study team will discontinue the study intervention in this participant.

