The study results will increase knowledge regarding how the SRD alters the urinary metabolome in pre-hypertensive patients, investigating associations of salt sensitivity and within- and between-person variations in the SRD intervention, and exploring how these alterations may improve BP control and cardiovascular health. Also, it will provide foundational information for future work on developing personalized nutrition interventions to reduce dietary sodium intake through identified mechanisms.

3. Objectives and Endpoints *All data points collected in the study should support an objective or have a regulatory purpose.* *Complete the table – add rows as needed.*

3.1. Objective(s) Clearly and concisely define the primary and secondary outcomes.	3.2. Endpoint Clearly define the endpoints. (endpoints are the basis for concluding that the objective has been met).	3.3. Justification for Endpoint Briefly explain why the endpoint(s) were chosen.

 To examine the associations of urine metabolites with urinary sodium levels and BP control. 	
 The metabolite profiles identified in this study will provide insight into the mechanisms underlying changes in sodium intake and BP levels in hypertension. 	
 Previous studies in our team found some novel metabolites which are reflecting dietary sodium intake using targeted urinary metabolites.

 To determine the feasibility, preliminary efficacy, and estimate of the effect size of sodium- 	
 Findings of the study will help develop effective interventions to improve sodium restricted 	
 Numerous studies have shown that low-sodium diet can reduce blood pressure and improve cardiovascular outcomes.

restricted diet intervention on changes in metabolomics profiling and BP reduction among 40 pre-hypertensive patients.	diet adherence and cardiovascular outcomes.	

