- Usual Care Control Group (CG): The 20 subjects will receive their routine medical and nursing care for pre-hypertension that consists of a recommendation to follow SRD and take medications as prescribed. Usual care consists of recommendations to follow an SRD, but without explicit skills training including instructions on gradual adaptation to sodium restricted diet, follow-up of progress or provision of monitoring. In addition, digital self-monitoring using Fitbit and its companion app, and wireless BP monitor will be used over 8 weeks.

8. Protocol-Directed procedures, items, services or tests

List all procedures directed by the study plan - including items or services provided as part of routine or conventional care and those needed to diagnosis or treat research related complications.

Important Note – The protocol directed procedures listed must match those in the [Schedule of Activities \(attachment\)](#)

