11.2. Continued Follow-up Discontinuation of Study Intervention

Describe efforts that will be made to continue follow-up of participants who discontinue the study intervention, but remain in the study for follow-up, especially for safety and efficacy study endpoints (if applicable). Reasonable efforts must be made to undertake protocol-specified safety follow-up procedures to capture adverse events (AE), serious adverse events (SAE), and unanticipated problems involving risks to subjects or others (UPIRSOs).

This is expected to be a minimum risk study with dietary interventions. All participants will be allowed to discontinue the study at any time. Despite study intervention termination, it is optional for participants to continue use mobile devices to monitor their health status.

12. Statistical Considerations

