12.1. Statistical Hypotheses

State the formal and testable null and alternative hypotheses for primary and key secondary endpoints, specifying the type of comparison (e.g., superiority, equivalence or non-inferiority, dose response) and time period for which each endpoint will be analyzed.

We hypothesize that compared with those in the control group (usual care), the subjects in the intervention group (modified Sodium Watcher Program-Hypertension) will show;

- Hypothesis 1: a trend for reduced urinary sodium excretion
- Hypothesis 2: a trend for improved BP control

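### Section 11.1's only stated response to a threatening home BP reading, high or low, is to stop the study intervention: a poor match for a high reading and no effective response in controls

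*Combined protocol and SAP*

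**What the plan says.** Section 11.1 describes the study as minimal risk, has BP monitored by mobile device, and names unusually low and unusually high pressure together as examples of a threatening reading. When such readings "are identified for a participant, the study team will discontinue the study intervention in this participant". It sets no mmHg limit, does not separate the two directions, and does not distinguish the arms.

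Section 11.2 covers what follows: "Despite study intervention termination, it is optional for participants to continue use mobile devices to monitor their health status". Section 10.4 states that there is no rescue medicine.

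The plan's expectation for BP is clear. Section 3.3 says: "Numerous studies have shown that low-sodium diet can reduce blood pressure and improve cardiovascular outcomes". Hypothesis 2 in section 12.1 expects "a trend for improved BP control" in the intervention group relative to usual care.

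Section 7 gives the intervention group eight weeks of sodium-reduction education with goal setting and digital self-monitoring. The control group has usual care, which includes advice to restrict sodium, "but without explicit skills training including instructions on gradual adaptation to sodium restricted diet, follow-up of progress or provision of monitoring". The study adds a Fitbit and a wireless BP monitor for controls too.

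Section 10.1 describes one kind of call to participants. In the intervention group, "The PI will remotely track user engagement and will call participants if they fail to measure any behavior for 3 days". In the control group, "The intervention nursing research assistant will remotely track user engagement and will call participants if they fail to measure any behavior for 3 days".

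**The concern.** A rule that treats high and low readings alike can fit only one of them. Stopping a sodium-reduction programme is a natural response to low pressure. After a high reading, it takes away something meant to bring pressure down and adds nothing that deals with the reading.

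People are enrolled because their pressure is raised (SBP 120-159 or DBP 80-99 mmHg, with or without medication, section 6.2) and record it at home for 8 weeks (section 8.6). High readings are therefore a foreseeable trigger, and they are the case that the rule serves worst. In the control group, 20 of the 40 participants, there is no programme to stop.

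What is at stake is the participant's safety after a worrying reading that the study itself has prompted and recorded.

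**Working it through.** The plan gives no BP limit, event rate or other figure for this rule, so there is nothing to recompute. The check takes each combination of arm and direction and asks what staff would do if they followed the text.

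1. **Low reading, intervention arm.** Section 11.1 stops the programme. Since the plan expects the programme to lower BP (section 3.3, Hypothesis 2), the action fits the reading. No contact or referral is stated.

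2. **High reading, intervention arm.** Section 11.1 again stops the programme. On the plan's own premise this removes a BP-lowering measure. Sodium advice under usual care and existing medication continue (sections 7 and 10.3), so what is lost is the sessions and goal setting. Nothing in the rule addresses the reading.

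3. **Low or high reading, control arm.** There is no sodium programme to discontinue (sections 5.1 and 7). Either the rule has no effect, or self-monitoring counts as the study intervention and the rule ends BP monitoring just after a threatening value. Neither is an effective response.

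4. **Contact and referral.** The calls in section 10.1 are triggered, in both arms, by three days without a measurement. No section says that a threatening value triggers a call, a repeat reading or a referral. As written, a gap in measurement leads to contact and a dangerous measurement is not said to.

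5. **After stopping.** Section 11.2 permits continued device use but does not ask for it. Section 10.1 says "Everyone will receive a baseline and end of study visits", which should cover stopped participants, but sections 11.1 and 11.2 do not say so.

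6. **Whether control readings reach the team.** The control-group paragraph of section 10.1 links each participant's devices to the platform and has staff track engagement, which implies that control data arrive. Yet its sentence on transmission names only the intervention group's data. This is probably a drafting slip. Read literally, a threatening control reading would not be seen at all.

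**The case against.** The strongest defence is that section 11.1 answers a narrow template question about criteria for discontinuation. It does not say that discontinuation is the only step, and an escalation procedure may sit in the attached Schedule of Activities or the consent pages. A reader might infer that the study has no escalation procedure at all. The documents do not support that, because those pages cannot be seen. What stands is narrower: the visible text states none, and the template prompt for section 11.1 asks for clinical decision points as well as stopping criteria.

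Second, the Background (section 2) says that individual responses to sodium restriction vary and that its benefit has been questioned. A threatening high reading on the programme could be a poor response, and returning that person to usual care is a defensible, cautious choice. This also stands in part. A reader might infer that stopping is plainly harmful or leaves the participant untreated; the variable response and the continuing advice and medication argue against both. It does not rescue the rule, because automatic stopping is stated without clinical judgement and does not address the reading.

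Third, the sessions are live video meetings, so staff could hardly stop them without speaking to the participant. That is fair for the intervention arm, but it has no counterpart among controls and does not bring in a clinician.

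**Conclusion.** The point holds as a minor safety defect. In the text available, one action serves four situations and fits one of them well: a low reading in the intervention arm. For a high reading in that arm it is mismatched and insufficient. In the control arm it gives no effective response.

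This rests on two conditions. The plan's own expectation that the programme lowers BP is taken at face value, and the unseen Schedule of Activities and consent pages are assumed not to contain an escalation step. If they do, the remaining task is for section 11.1 to refer to it and to stop treating high and low readings alike.

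The number of participants affected cannot be given: the plan states no limit and no reading-to-reading variability. A reader might infer that the rule biases the BP comparison between arms. The documents give no basis for sizing or asserting that, and no effect on the trial's estimates is claimed here.

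**What to change.** - **Section 11.1, both arms:** have a clinician set high and low limits. When a reading passes either, the staff who already make calls under section 10.1 contact the participant promptly and refer to the treating clinician.
- **Section 11.1, intervention arm:** after a low reading, pause the sodium goal. After a high reading, do not stop the programme automatically; continue it unless the clinician advises otherwise.
- **Section 11.2:** make continued home BP monitoring the default, with freedom to decline, and state that stopped participants keep the end-of-study visit.
- **Section 10.1, control paragraph:** correct the transmission sentence so that control readings plainly reach the team.
- If the Schedule of Activities or consent form already has an escalation step, cite it in section 11.1.

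The cost is a short amendment and some extra calls and referrals, expected to be few. Their number depends on the limits chosen and cannot be estimated from the documents. The devices, the platform and the calling staff are already in place. If control data are in fact not transmitted, connecting them would be an added task. No extra participants are needed.

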11.2. Continued Follow-up Discontinuation of Study Intervention

Describe efforts that will be made to continue follow-up of participants who discontinue the study intervention, but remain in the study for follow-up, especially for safety and efficacy study endpoints (if applicable). Reasonable efforts must be made to undertake protocol-specified safety follow-up procedures to capture adverse events (AE), serious adverse events (SAE), and unanticipated problems involving risks to subjects or others (UPIRSOs).

This is expected to be a minimum risk study with dietary interventions. All participants will be allowed to discontinue the study at any time. Despite study intervention termination, it is optional for participants to continue use mobile devices to monitor their health status.

12. Statistical Considerations

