8.2. Devices

All health devices, including fitness tracker and wireless BP monitor will be provided to each participant by the study team.

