8.6. Other Research Procedures (e.g., other safety and efficacy assessments.)

Digital self-monitoring for diet and in-home monitoring of BP will be recorded automatically via wearable fitness tracker and wireless BP monitor over 8 weeks. The following data will be collected by self-reported questionnaire or relevant health equipment. Informed consent will be obtained either at pre-study visit (Day -1) or baseline visit (Day 1).

- Individual characteristics (baseline): We will collect demographic information such as age and gender.
- Physical Assessment (baseline and 8-week): Height, weight, and blood pressure will be measured at baseline and 8-week.

8.7 Attach a Schedule of Activities (SOA) Excel File [Download the Template here: [Schedule of Activities](#)]

Check to indicate that the SOA Excel File is attached →

9. Preparation/Handling/ Storage/Accountability of Investigational Drug, Biologic, or Device

N/A - This study does not include any investigational products (e.g. drugs, devices or biologics)

N/A - An Investigator Brochure is attached

N/A - A Drug/Device Manual is attached

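### Section 11.2 makes home BP monitoring optional after any stop, with no exception for participants stopped because of a threatening home BP reading

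*Combined protocol and SAP*

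**What the plan says.** **The safety monitor.** Section 11.1 says that participants' "blood pressure will be monitored by mobile device". If a reading is unusually low or high and may endanger the participant, "the study team will discontinue the study intervention in this participant". That is the only action stated.

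**After a stop.** Section 11.2 gives one rule, whatever the reason for stopping: "Despite study intervention termination, it is optional for participants to continue use mobile devices to monitor their health status". The form's prompt for that section asks for reasonable efforts at safety follow-up. The answer names none.

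**Before a stop.** Under section 10.1 both arms are instructed to log home BP, and staff "will call participants if they fail to measure any behavior for 3 days". In the control arm this is a research assistant's task: "The intervention nursing research assistant will remotely track user engagement". Section 8.6 describes home BP recording over 8 weeks.

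**Study-measured BP.** Section 8.6: "Height, weight, and blood pressure will be measured at baseline and 8-week". Section 10.1: "Everyone will receive a baseline and end of study visits". No study BP between these two points appears in the visible text.

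**The concern.** The device that detects a possible danger is the one whose use becomes optional once the danger has been detected. Optional use is sensible for someone who leaves the programme for lack of time or interest. It is a poor rule for someone stopped because a reading looked threatening, since the open question is then whether BP has resolved, persisted or worsened.

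Eligible participants may be taking BP medication (section 6.2) and stay on it (section 10.3). A worrying reading may therefore need a treating clinician's decision. Ending a diet-education programme does not supply that decision, and no step in the visible text passes the reading to a clinician. At stake is the safety follow-up of a few people.

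**Working it through.** The plan gives no figure to reproduce. The check sets the sections side by side and then does simple timing and probability arithmetic.

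**Step 1. What changes at a stop**

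| | Before a stop | After a BP-triggered stop |
|---|---|---|
| Home BP | Instructed to log (10.1) | Optional (11.2) |
| Call after 3 days without data | Yes, both arms (10.1) | Not stated |
| Repeat reading or referral | Not applicable | Not stated |
| Study-measured BP | Baseline, week 8 (8.6) | Week 8 (8.6), if the participant stays in |

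Section 11.2 refers to mobile devices in general. Section 11.1 says BP is monitored by mobile device, so the BP monitor is included.

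**Step 2. Time to the next scheduled study BP**

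Taking week 8 as day 56, a stop on day d leaves a gap of 56 − d days.

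- d = 14: 56 − 14 = 42 days (42/56 = 75% of the monitoring period)
- d = 28: 56 − 28 = 28 days (50%)
- d = 42: 56 − 42 = 14 days (25%)
- Stops spread evenly over days 1 to 55: mean gap (1 + 55)/2 = 28 days, maximum 55

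This step needs no assumed event rate.

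**Step 3. How likely the rule is to be used**

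Section 11.1 gives no BP cut-off and no expected stop rate, so the per-person probability p is an assumption. The number who can be stopped, n, is also open. Only the 20 intervention participants have an education programme to stop. Both arms, however, carry digital self-monitoring in their group names (section 5.1), so all 40 is a possible reading.

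P(at least one stop) = 1 − (1 − p)^n; expected stops = np.

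| Assumed p | n = 20: P (expected) | n = 40: P (expected) |
|---|---|---|
| 1% | 18% (0.2) | 33% (0.4) |
| 2% | 33% (0.4) | 55% (0.8) |
| 5% | 64% (1.0) | 87% (2.0) |
| 10% | 88% (2.0) | 99% (4.0) |

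For example, 1 − 0.99^20 = 0.18 and 1 − 0.90^40 = 0.985.

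**Step 4. Monitoring that a fix would retain**

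Retained participant-days = np × 28, out of 40 × 56 = 2,240 planned.

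- n = 20: 0.2 × 28 = 5.6 to 2.0 × 28 = 56 days (0.25% to 2.5%)
- n = 40: 0.4 × 28 = 11.2 to 4.0 × 28 = 112 days (0.5% to 5%)

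**The case against.** **The contrast between before and after is softer than it looks.** This stands in part. No home BP frequency is set before a stop, and section 12.4 counts the percentage of days with a BP log as a feasibility measure, so gaps are expected. The sentence in 11.2 can be read as an offer to keep monitoring. Nothing says that devices are returned, transmission ends or calls cease. A reader might infer that monitoring is strictly required and is then switched off; the documents do not support that. What changes is narrower: an instruction backed by a call becomes an option, with the call left unstated.

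**Sections 8.6 and 10.1 already cover the 8 weeks.** Neither is expressly suspended, but 11.2 is the specific rule for people who have stopped. The 3-day call responds to missing data and is not described as follow-up of an abnormal reading.

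**Unseen material may fill the gap.** The Schedule of Activities is a separate attachment, and the consent pages are not shown. Either could contain a BP check or advice on abnormal readings. This stands, and it limits the point to the visible text. The form does require section 8 to match the schedule, and section 8 lists no such check.

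**Usual medical care continues.** It does, and the trial does not replace the treating clinician. But no step ensures that the clinician learns of the reading.

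**The trigger has no cut-off.** True, so stops may not be applied consistently. The proposed rule can still operate, because it attaches to the team's own decision to stop for BP.

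**The trial is low risk and small.** This bears on how often the rule will be used. Section 11.1 nevertheless foresees readings that may threaten health.

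A reader might also infer that week-8 BP or the feasibility results are biased. The documents give no basis for that.

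**Conclusion.** The point holds in a limited form. Section 11.2 states a rule that, if followed, gives weaker follow-up to the participants whom section 11.1 has identified as possibly at risk. Someone stopped for BP may go 42, 28 or 14 days (stop on day 14, 28 or 42) before the next scheduled study BP, with no repeat reading or referral written down.

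The timing rests on taking week 8 as day 56, on the visible text being complete on this matter, and on the participant staying in the study to week 8. The frequency cannot be derived. The chance of at least one such stop, 18% to 88% with 20 at risk or 33% to 99% with 40, rests wholly on assumed per-person rates of 1% to 10%; it illustrates that the rule could matter and does not predict how often.

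This is a cheap improvement to safety follow-up. It does not affect the validity of the pilot's results.

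**What to change.** Replace the optional-device sentence in section 11.2 with wording such as:

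*Participants whose study intervention is stopped because of BP are asked to take a prompt repeat home reading and are referred to their treating clinician. They are asked to continue home BP monitoring, with the existing 3-day missed-reading call, until week 8 or until the clinician advises otherwise, and to complete the week-8 visit unless they withdraw. Device use is optional for participants who discontinue for other reasons.*

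**Cost.** A few sentences. The equipment is already in place (section 8.2: "All health devices, including fitness tracker and wireless BP monitor will be provided to each participant by the study team"), and section 10.1 describes the platform and the call for both arms. The retained monitoring, 5.6 to 112 participant-days across the assumed range, falls within the 8 weeks already planned. The downside is a small burden on the few stopped participants, who can still withdraw, and staff time for the referral.
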